##### **4.1. Inclusion Criteria**

Subjects must meet all of the following inclusion criteria to be eligible for inclusion into the study:

1. Female
2. At least one prescription for bazedoxifene, raloxifene, or any bisphosphonate during the study inclusion period (index prescription);
3. A recoded diagnosis code of osteoporosis on or within 60 days prior to the index prescription date;
4. Age  $\geq 45$  at the date of the index prescription; and
5. At least 6-months of follow-up data in the electronic medical record system prior to the date of the index prescription

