* Due to low enrolment/accrual into the study, the original end of the study accrual period was extended from September 30th 2012 in Spain, and April 30th 2013 in Italy, to April 30th 2014 for both Spain and Italy. Extending the accrual period to April 2014 extended the study timelines by 1 year. The new accrual period for Spain is 43 months (October 1st 2010-April 30th 2014) and the new accrual period for Italy is 36 months (May 1st 2011-April 30th 2014).

Patients will be counted in according to the inclusion criteria.

Follow up for each endpoint will be from the index date to whichever of the following occurs first.

1. Endpoint under investigation
2. Last patient visit or completion of 5 years follow up, whichever occurs first.

Each patient will be followed for identification of selected endpoints for a period of up to five years from their index prescription date for BZA, bisphosphonate or raloxifene. The follow up will continue even if the woman discontinues the index medication or switches to a different medication during this five year follow up period. The follow up duration of an individual patient may be shorter than five years if the woman transfers out of the GP office that wrote the index prescription or if she dies.¹ In these situations the data will be censored on the date of last visit. This study will use the Cegedim Longitudinal Patient Database (LPD), an electronic medical records database. However, the Spanish and Italian databases of Cegedim Strategic Data (CSD) do not have recorded events of death and date of death. The discontinued patient's record indicate loss to follow-up for various reasons, such as patients' moving from the areas, patient's change of GPs or other various reasons. The number of patients who are lost to follow-up will be provided. A minimum of a six month history in the LPD database prior to the index date (at least one GP visit, whatever the motive of the visit to GP) is required for inclusion of population, in order to ensure a certain quality of information.

Study Population

The study population will be selected based on the following inclusion criteria and all eligible patients enrolled in this study will be included. No exclusion criteria were applied.

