Any patient with a prescription for BZA (exposed cohort), raloxifene (comparator cohort) and bisphosphonate (comparator cohort) treatment accompanied with diagnosis of osteoporosis will be eligible when they meet other inclusion criteria. The detailed inclusion criteria will be as follows:

1. *Female*
2. *At least one prescription for BZA, raloxifene, or any bisphosphonate during the study inclusion period*
3. *A recorded diagnosis code of osteoporosis on or within 60 days prior to the index prescription date.*
4. *Age of patients ≥ 45 at the index prescription date*
5. *At least 6 months of follow-up data in the electronic medical record system prior to the date of index prescription.*

¹ The event of death and date of death are not recorded in CSD Italian and Spanish database. The discontinued patient's records indicate loss to follow-up for various reasons.

The applicability of the third criterion will be evaluated through performing a sensitivity analysis comparing those with osteoporosis diagnosis within 60 days and those without diagnosis within 60 days. This has become necessary due to a significant number of patients (> 45%) missing a recorded diagnosis of osteoporosis. If the venous thromboembolism rates of the two groups are comparable (i.e., difference within 20%), this criterion will not be included.

Data Source

This study will use the Cegedim Longitudinal Patient Database (LPD), an electronic medical records database that collects clinical data from primary care physician practices in the following European countries i.e., Spain, Italy, Germany, France, Belgium and UK. (In the UK the database is known as The Health Improvement Network (THIN).) For this study the Cegedim LPD in Italy and Spain will be used.

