8.1.4 TIME TO EVENT ANALYSIS

A time to event analysis to compare the risk between treatment cohorts, i.e., the BZA, raloxifene and bisphosphonate treated groups, will be conducted for the primary end point (VTE) and other secondary endpoints if sufficient data are available,

[figure not shown]
The time to an event will be calculated as the time from index prescription date to the incidence date of primary end points. If a patient does not have a primary end point, the treatment duration will be based upon the index prescription date to the last visit or end of follow-up period, whichever comes first.

In order to ensure the exact duration from the start of treatment to the incidence of primary endpoints, a subgroup of newly prescribed patients who were diagnosed with osteoporosis during the enrolment period will be used first.

In the very unlikely event that the number of bisphosphonate or raloxifene patients are less than the number of BZA patients, the analysis will be extended to include bisphosphonate and raloxifene patients whose treatment began prior to the enrolment period. Considering the fact that bisphosphonates and raloxifene were launched before BZA (See the figure below), some patients could have already gotten treatment of bisphosphonates and raloxifene prior to the enrolment period (i.e., before BZA was launched). For such patients the start date will be the first date of treatment for bisphosphonates or raloxifene, available within the database.

Figure 1. Calculation of duration (from start date to the incidence of primary endpoint) for the treatment cohorts

The time to event analysis model will also be used to test for differences in time to event while adjusting for covariates of interest.

This model will take into account the duration to the incidence of the endpoint and control for imbalances in outcome risk factors, as determined based on the baseline descriptive analysis.

The following factors possibly related to the incidence of the primary end point will be considered.

- Treatment group (BZA, raloxifene, and bisphosphonate)
- Age
- BMI
- Reported history of smoking (If the reported frequency of smoking status is low this will be excluded)
- Reported Medical History of Diabetes, Hypertension, Malignancies
- Time since diagnosis of osteoporosis
- Previous treatment for osteoporosis (before index date) or Number of different treatments for osteoporosis in the entire patient history available
- History of DVT or PE

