8.2 STATISTICAL ANALYSES

8.2.1 PATIENT CHARACTERISTICS

Descriptive statistics on available patient characteristics (e.g. age, BMI, smoking, history of relevant medical diagnoses) will be reported for all exposure groups at index date. A summary table will present and compare all the patients' demographic data at index date (BZA/raloxifene/bisphosphonates).

- Age (years): derived by difference between the year of time of interest and year of birth.
- Weight (kg): recorded at the given date, or if not available, at the most recent date before or it
- Height (cm): the value at the given date or, if not available, at the most recent date before or after it.

- Body Mass Index (BMI) (kg/m^2), calculated from weight and height as defined previously. BMI will be described in quantitative measure and in categorical data, as usual
- Alcohol use
- Smoking status
- Time since diagnosis of osteoporosis: derived by the difference between the index date and the diagnosis date.
- Previous treatment for osteoporosis (before index date) (yes versus no) or Number of different treatments for osteoporosis in the entire patient history available
- Previous history of VTE (Venous Thromboembolic Events) (before index date)
- Previous history of major lower extremity (hip, knee) arthroplasty, arthroscopic surgery (information on arthroscopic surgery not available in Italian database)
- General surgery, major orthopedic surgery (<1month prior to incidence of VTE) (information on general surgery not available in Italian database)
- Multiple trauma, (<1month prior to incidence of VTE)
- Hip, pelvis, or leg fracture (<1month prior to incidence of VTE)
- Stroke (<1month prior to incidence of VTE)
- Acute spinal cord injury (paralysis) (<1month prior to incidence of VTE)
- Hormone replacement therapy (limited information available in both databases)

If the diagnoses for any of the conditions listed in this section (8.2.1) are not found in the database, they will be assumed to be absent.

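### SAP 8.1.4 selects the time-to-event population by an osteoporosis-diagnosis rule that conflicts with sections 2.1, 5.4 and 8.2.5 and, if inclusion criterion 3 is dropped, lets in codes recorded after index

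*SAP*

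**What the plan says.** Four parts of the SAP bear on who enters the VTE hazard ratio.

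- **Section 2.1 (criterion 3, as in Protocol 4.1):** "A recorded diagnosis code of osteoporosis on or within 60 days prior to the index prescription date". The SAP then makes this provisional: "If the venous thromboembolism rates of the two groups are comparable (i.e., difference within 20%), this criterion will not be included". The reason given is "This has become necessary due to a significant number of patients (> 45%) missing a recorded diagnosis of osteoporosis".
- **Section 8.1.4:** to fix the exact duration from start of treatment to event, "a subgroup of newly prescribed patients who were diagnosed with osteoporosis during the enrolment period will be used first". The only stated extension applies if a comparator group is smaller than the bazedoxifene (BZA) group: "the analysis will be extended to include bisphosphonate and raloxifene patients whose treatment began prior to the enrolment period".
- **Section 8.2.5:** the Cox hazard ratio for VTE is assigned to the full BZA and raloxifene cohorts with the age-stratified bisphosphonate sample, and to the incident-user subgroup. Section 5.4 defines incident users by six months without osteoporosis treatment and sets no diagnosis condition.
- **Covariates:** 8.1.4 lists time since diagnosis among the factors to be considered, subject to a univariate screen at p ≤ 0.20. Section 8.2.1 defines it: "Time since diagnosis of osteoporosis: derived by the difference between the index date and the diagnosis date". Section 7 exempts the osteoporosis diagnosis from the rule that an unrecorded condition is absent, and plans imputation only for BMI, smoking and alcohol.

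**The concern.** SAP 4.2 and 8.2.2 make the Cox hazard ratio the statistic for comparing event rates, and 8.1.4 is where that model is specified. If 8.1.4 and 8.2.5 describe different women, the analyst can choose the population after seeing the data, and the incidence rates and the hazard ratio may describe different groups.

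The diagnosis wording in 8.1.4 is tied neither to the index date nor to the 20% rule. Were criterion 3 dropped, a woman could qualify on a code entered long after follow-up began. To receive it she must have stayed under observation in the practice. Women who left earlier cannot qualify, nor can women who died, and SAP 2.1 says these databases do not record deaths. A late code also gives a negative time since diagnosis, and no code gives no value at all.

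**Working it through.** **Which women each section admits**

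| | Criterion 3 kept | Criterion 3 dropped |
|---|---|---|
| 2.1 | Code on index date or in the 60 days before | No code needed |
| 8.1.4 | Code within enrolment period, newly prescribed | Same wording: code still needed, at any time in enrolment |
| 8.2.5 and 5.4 | Full cohorts or incident users, all coded by index | Full cohorts or incident users, coded or not |

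If criterion 3 is kept, every woman already has a code by index. The diagnosis condition in 8.1.4 then removes few women, for example those coded before enrolment opened and indexed in its first 60 days. If it is dropped, the sections part. Enrolment runs 43 months in Spain and 36 in Italy (SAP 2.1), so a Spanish woman indexed at the start could qualify on a code up to about 43 months later. The fallback extension does not repair this: it adds earlier-treated comparator women, does not lift the diagnosis condition, and adds no BZA women.

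**Time since diagnosis if criterion 3 is dropped**

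Index date minus diagnosis date is negative for a post-index code and undefined without a code. Section 8.2.1 does assume unrecorded diagnoses absent, but that supplies no date. If the factor passes the screen, a standard complete-case fit would delete uncoded women.

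**Reproducing the plan's precision**

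Inputs: comparator rate 1.74 per 1,000 person-years (PY), follow-up to 5 years, 15% loss, Wald 95% intervals (Protocol 7.1).

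E = n × PY × 0.00174 (× ratio for BZA); SE = √(1/E_BZA + 1/E_bis); interval = ratio × exp(±1.96 SE).

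Protocol Table 3, 1:6 row (1,750 vs 10,500), states 0.6-1.8, 0.9-2.5 and 1.3-3.1 at ratios 1, 1.5 and 2.

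- 4.25 PY (5 × 0.85, loss taken once): 0.56-1.80, 0.91-2.47, 1.28-3.12. This matches.
- 3.42 PY (15% lost every year, (1 − 0.85⁵)/(−ln 0.85)): 0.52-1.93, 0.86-2.61, 1.22-3.28. This does not match.

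The product of rate and PY sets the width, so 4.25 PY is not the only possible explanation. Both values are carried forward.

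**Precision if only coded women remain**

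Assumptions: the 1,823 BZA and 10,938 bisphosphonate women (SAP 5.4) include uncoded women, and 45% are lost in each arm. That leaves 1,823 × 0.55 = 1,003 and 10,938 × 0.55 = 6,016.

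At ratio 2 and 4.25 PY:

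- Full: E = 27.0 and 80.9, SE = 0.222, interval 1.29-3.09.
- Coded only: E = 14.8 and 44.5, SE = 0.300, interval 1.11-3.60.

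| PY | Ratio | Full | Coded only |
|---|---|---|---|
| 4.25 | 1 | 0.56-1.78 | 0.46-2.18 |
| 4.25 | 1.5 | 0.92-2.44 | 0.78-2.89 |
| 4.25 | 2 | 1.29-3.09 | 1.11-3.60 |
| 3.42 | 1 | 0.53-1.90 | 0.42-2.38 |
| 3.42 | 1.5 | 0.87-2.58 | 0.72-3.12 |
| 3.42 | 2 | 1.23-3.25 | 1.04-3.85 |

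The log-scale width grows by 1/√(1 − loss): 1.00 for no loss, 1/√0.80 = 1.12 for 20%, 1/√0.55 = 1.35 for 45%. Refilling the bisphosphonate sample to 10,938 with coded women (82,041 × 0.55 ≈ 45,120 would be available) gives 1.15-3.48 at ratio 2 and 4.25 PY. This helps little, because BZA events limit precision.

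**The case against.** A reader might infer that the hazard-ratio population is certain to shrink by about 45%. The documents do not support that, for four reasons.

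- Section 8.2.5 names the populations for this Cox test, and none is restricted to diagnosed women beyond the inclusion criteria. Section 8.1.4 says its subgroup comes first, not that it is the only one. This stands against certain shrinkage, but it leaves two incompatible instructions in one SAP.
- Criterion 3 applies by default. Post-index codes, negative durations and uncoded women arise only if the 20% rule removes it, and neither document says which way that went. This stands. The removal is nonetheless a planned branch, and 8.1.4 has no wording for it.
- Time since diagnosis is only a candidate. Women drop out through it only if criterion 3 goes, the factor passes the screen, and missing values are deleted by default. This stands.
- SAP 5.1 defines the full analysis set as women meeting the inclusion criteria. If the 1,823 already meet criterion 3, missing codes remove nobody. The 45% is also not split by arm and may mean no code in the 60-day window rather than no code at all; under the latter reading of 2.1's window, the wider 8.1.4 window could recover some women. This stands and makes every loss figure conditional.

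Nor should late-coded women be called event-free. A non-fatal VTE does not prevent a later code, so the selection is on staying under observation.

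**Conclusion.** The point holds as a conflict between sections with a conditional cost. Sections 2.1, 8.1.4 and 8.2.5 with 5.4 do not give one population for the VTE hazard ratio, and nothing says what 8.1.4 becomes if criterion 3 is dropped. In that branch, following 8.1.4 literally conditions entry on information recorded after follow-up began and leaves time since diagnosis undefined for uncoded women.

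The cost in precision lies between nothing, if the stated counts already meet criterion 3, and a log-scale interval 1.35 times as wide, if they include uncoded women and 45% are lost equally from both arms. At a ratio of 2 all the intervals shown still exclude 1, but at 3.42 PY the lower limit falls to 1.04. The share without a code is stated only as above 45%, so a larger loss cannot be excluded. The new-user restriction would cut numbers further and is not counted here. The size and direction of any bias from late codes cannot be worked out from the documents.

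**What to change.** 1. In SAP 8.1.4, replace the diagnosis condition with *meeting the section 2.1 inclusion criteria as finally applied*, and define newly prescribed by the incident-user rule in 5.4.
2. Have 8.1.4 and 8.2.5 name the same hazard-ratio populations under each outcome of the 20% rule.
3. State that a diagnosis coded after index is never used to select women or to derive a covariate.
4. If criterion 3 is dropped, replace time since diagnosis with a categorical variable that has a level for no diagnosis recorded by index, so that no woman is deleted for lacking a date.
5. State whether the 1,823 and 82,041 already meet criterion 3, so that the effect on precision is known.

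The cost is SAP wording and one recoded covariate. The small downside is a coarser adjustment for osteoporosis duration.

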The Cegedim LPD obtains medical information from proprietary practice management software used during physician office visits to capture clinical data in an electronic medical record system. Physicians use the practice management software developed by Cegedim to maintain electronic medical records of their patients. In each country a panel of physicians using this electronic system volunteered to make available anonymized patient-level information from their practices for clinical research purposes. Since these data are being collected in usual clinical care in a non-interventional way, they reflect routine clinical practice in these countries. The panel of contributing physicians is maintained as a representative sample of the primary care physician population in each country according to age, sex, and geographical distribution. Additionally in most countries (including Spain and Italy), the patient population is representative of the respective country population according to age and sex distribution, as provided by national statistic authorities.

Table 2: Doctor and patient populations in the Cegedim LPD by country

	Italy	Spain
Number of physicians in the panel	700	300
Average number of patients who consulted GP at least once in a year	800,000	320,000

The patient data in the LPD form a nationally representative sample. Data have been collected in Italy since 2004 and in Spain since 2006, providing several years of medical history, including comorbidity and concomitant medication use information. Of the patients included in the Spanish and Italian LPD, there are currently approximately 68,000 women with drug-treated osteoporosis. Between 1 and 6% of these patients are taking raloxifene, depending on the region; most of the rest are prescribed a bisphosphonate (Cegedim, data on file).

Data are entered regularly during usual patient care, submitted daily to the Cegedim coordinating center, cleaned and de-identified, and then made available for research.

Anonymized patient data collected from each GP practice includes:

- *Demographic information (age, gender)*
- *Medical history (event dates, diagnoses, risk factors, referrals to specialists)*
- *Therapeutic history (date/length of prescription, molecule/product, dosage)*
- *Additional information (test results, immunizations, height, weight, blood pressure)*

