5.4 SUBGROUPS

Age stratified randomly selected subgroup

In the current dataset, there are 1,823 patients in the bazedoxifene group and 82,041 patients in the bisphosphonate group. This means that there is more than 40 times the number of subjects in the bisphosphonate group compared to the number of subjects in the bazedoxifene group. To limit the number of patients in the bisphosphonate group, an age stratified random subgroup will be selected. Based on the sample size and relative risk estimates provided in the final study protocol (study protocol section 7.1, Sample size calculation), the 1,823 bazedoxifene subjects will be adequately matched by a ratio of 1:6 bisphosphonate subjects. Therefore $1,823 \times 6 = 10,938$ bisphosphonate treated subjects are needed to be randomly selected from the total of 82,041 bisphosphonate treated subjects.

Selection scheme: The age of subjects in the study will be categorized into 4 groups (45-49, 50-59, 60-69, and ≥ 70). In the bisphosphonate group, the percentage of subjects in each of these age groups is 1.4%, 13.7%, 28.7%, and 56.2% respectively. To maintain the same proportion of subjects in each age group for the bisphosphonate subgroup, there will be $1.4\% \times 10,938 = 153$ bisphosphonate treated subjects randomly selected from the 45-49 age group; $13.7\% \times 10,938 = 1,499$ subjects randomly selected from the 50-59 age group; $28.7\% \times 10,938 = 3,139$ subjects randomly selected from the 60-69 age group; $56.2\% \times 10,938 = 6,147$ subjects randomly selected from ≥ 70 age group.

Incident cases of study endpoints

Women with a history of study end points recorded prior to the index prescription will not be included in the analysis for that specific outcome, but will be analyzed separately as subgroups for each study end point. The analyses of the primary and secondary endpoints will be performed using these incident cases of study endpoints subgroups.

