8 STATISTICAL METHODOLOGY AND STATISTICAL ANALYSES

8.1 STATISTICAL METHODS

Analyses will be conducted separately for each country and the final report will consist of three parts: one part for Italy, one part for Spain, and the final part with pooled data of both countries. Pooling of data for the combined results of Italy and Spain will be done at the patient level. ICD9 codes of the Italian data will be mapped unto ICPE codes of the data from Spain. ICD9 codes that do not map directly to ICPE will be noted and the frequency of patients with outcomes in these unmapped categories will be reported. Given the very low enrolment from Italy (approximately 40 patients, vs. approximately 1700 from Spain) very few patients/outcomes from Italy are likely to be reported as unmapped. Assessment and adjustment for confounding will be done separately for each country and also done separately for the pooled analyses and follow the same methodology in the individual and pooled analyses. All statistical analyses will be performed using the SAS software 9.2, running with SAS Enterprise Guide 4.3, on a Windows Server.

The qualitative variables will be described by using usual statistics: population size and percentages (relative to the non-missing data) for each modality. Quantitative variables will be described with the number of observed data, mean, standard deviation (SD), median, and ranges. Two-sided 95% confidence intervals will be presented for relevant variables.

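### SAP 8.1.4 fallback: a shortage of either comparator adds pre-enrolment users of both, so too few raloxifene women would mix prevalent users into the new-user BZA-bisphosphonate Cox analysis

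*SAP*

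**What the plan says.** To get an exact duration from start of treatment, SAP 8.1.4 says that "a subgroup of newly prescribed patients who were diagnosed with osteoporosis during the enrolment period will be used first". The fallback follows. Its condition is "In the very unlikely event that the number of bisphosphonate or raloxifene patients are less than the number of BZA patients" and its consequence is that "the analysis will be extended to include bisphosphonate and raloxifene patients whose treatment began prior to the enrolment period". Time zero also moves for the added women: "For such patients the start date will be the first date of treatment for bisphosphonates or raloxifene, available within the database".

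No raloxifene count is given. The relevant figures elsewhere in the SAP are:
- 5.4: "there are 1,823 patients in the bazedoxifene group and 82,041 patients in the bisphosphonate group", with a 1:6 age-stratified sample of 10,938 bisphosphonate women.
- 2.1: "there are currently approximately 68,000 women with drug-treated osteoporosis" in the Spanish and Italian databases. "Between 1 and 6% of these patients are taking raloxifene, depending on the region".
- 2.1: more than 45% of patients lack a recorded osteoporosis diagnosis (group not specified).
- 8.1: analyses are run by country and pooled. Enrolment is given as "approximately 40 patients, vs. approximately 1700 from Spain" (Italy first), which from its size can only be the BZA group.

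On the standing of the analysis, 4.2 and 8.2.2 use the Cox hazard ratio to compare event rates, 8.1.2 makes cumulative incidence primary, and 8.2.4 calls time-to-event secondary. For the VTE objectives, 8.2.5 lists population (a), the full BZA and raloxifene cohorts with the bisphosphonate sample, and population (b), the incident-user subgroup of 5.4.

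**The concern.** The condition is joined by *or* and the consequence by *and*. The BZA-raloxifene comparison belongs to secondary objective 1 and the BZA-bisphosphonate comparison to the primary objective. A shortage that matters only to the first would change the comparator of the second.

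Women already on treatment before enrolment have come through the start of therapy without leaving the cohort. Adding them changes what the hazard ratio measures and opens it to selection of survivors. BZA women cannot have such history, because enrolment starts at BZA's launch in each country. The bisphosphonate comparison would take on that bias with no shortage to repair.

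The rule would be harmless if it could hardly ever be invoked, so the question is whether the plan's own figures support *very unlikely* for raloxifene.

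**Working it through.** **1. Reproduce the plan's figures (SAP 5.4).** 1,823 × 6 = 10,938, as stated. 82,041 / 1,823 = 45.0, consistent with more than 40 to 1.

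**2. Can bisphosphonates run short?** Only if the qualifying fraction is below 1,823 / 82,041 = 2.2%, or 1,823 / 10,938 = 16.7% if counted within the sample. For bisphosphonates the plan's description is fair.

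**3. Can raloxifene run short, counting users of all durations?**
- 68,000 × 1% = 680 and 68,000 × 6% = 4,080, against 1,823.
- Break-even share: 1,823 / 68,000 = 2.68%.
- Scaled to the accrued dataset (assumption: bisphosphonates are nearly all the rest), users = 82,041 × r / (1 − r), which is 829 at 1% and 5,237 at 6%. Break-even: 1,823 / (1,823 + 82,041) = 2.17%. A flat scaling factor of 1.25 gives 1,823 / 85,000 = 2.14%.

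Below about 2.1-2.7%, even all raloxifene users are fewer than the BZA women.

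**4. Apply the new-user restriction.** The SAP gives no qualifying fraction for either drug, so the table shows the fraction of raloxifene users that must qualify to avoid the trigger, with the scaled base in brackets. The second column counts all BZA women. The third assumes that half qualify (1,823 × 0.5 = 912).

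| Raloxifene share | Users | Needed v 1,823 | Needed v 912 |
|---|---|---|---|
| 1% | 680 (829) | not attainable | not attainable |
| 3.5% | 2,380 (2,976) | 77% (61%) | 38% (31%) |
| 6% | 4,080 (5,237) | 45% (35%) | 22% (17%) |

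If both drugs have the same qualifying fraction it cancels, and the break-even share stays at 2.1-2.7%.

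**5. Spain alone.** Assumption: the pool splits by GP patients, 320,000 / (320,000 + 800,000) = 28.6%. Then 68,000 × 0.286 gives about 19,430 women, and 1-6% of them is 194-1,166 raloxifene users (237-1,496 scaled), against about 1,700 BZA women. If all BZA women are counted, the trigger fires over the whole 1-6% range. If the BZA count is also restricted, the answer again depends on unstated fractions.

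**6. The protocol's own scenario.** Table 4 in Protocol 7.1 plans BZA and raloxifene at 2,150 each. Equal arms lie on the boundary of the trigger before any new-user restriction.

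**The case against.** The strongest reply is that the rule sits in a limited place. Population (a) is not restricted to new users, so no new-user restriction exists there to lose. Population (b) is listed separately for the same objective, and neither 5.4 nor 8.2.5 mentions the fallback. Cumulative incidence is the primary analysis, and previous osteoporosis treatment is a candidate covariate in 8.1.4. All of this stands. A reader might infer that the fallback undoes the new-user design of the primary comparison as a whole. The documents do not support that: they show only that the 8.1.4 Cox analysis is affected. They would support more if the newly prescribed subgroup of 8.1.4 were the same as population (b), but the SAP does not say so.

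A second reply is that the sentence may be meant comparator by comparator, and that it does not say whether the patients counted are newly prescribed or all enrolled, or which BZA count applies. That is fair. It makes the rule ambiguous, and an ambiguous rule still needs fixing. The literal wording extends both comparators.

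Third, the 1-6% share is regional and from one point in time. The SAP is dated 2016, after accrual closed, so its authors may have known the raloxifene count. This also stands: *very unlikely* is unsupported by what is written, but not disproved. Nor can one say that the trigger must fire at, for example, a 3% share. With a flat factor of 1.25 and an assumed 30% of raloxifene users qualifying, 68,000 × 3% × 1.25 × 0.30 = 765. That is below 912, but it is no shortage if fewer than 765 / 1,823 = 42% of BZA women qualify.

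**Conclusion.** The point holds for the 8.1.4 Cox analysis. As written, a raloxifene shortage alone brings pre-enrolment bisphosphonate users into a BZA-bisphosphonate comparison that has about 45 bisphosphonate women per BZA woman. That hazard ratio matters because 4.2 and 8.2.2 use the Cox model for the comparison, even though 8.2.4 labels time-to-event secondary.

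A raloxifene shortage is quite possible on the plan's figures. It is certain below a share of about 2.1-2.7% if all BZA women are counted, or if both drugs have the same qualifying fraction. Above that it depends on new-user fractions and a BZA count that are not given. The Spanish analysis looks most exposed, subject to the assumed split of the pool. The size of any resulting bias in the hazard ratio cannot be derived from the documents.

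**What to change.** Reword the fallback in SAP 8.1.4 so that:
- the trigger is applied separately to BZA-bisphosphonate and to BZA-raloxifene;
- both counts in each trigger are of women who meet the same newly-prescribed-and-diagnosed filter, with a statement of whether the trigger is assessed by country, pooled, or both;
- a raloxifene shortage extends only the BZA-raloxifene analysis, and the newly prescribed BZA-bisphosphonate result is kept and reported whatever the raloxifene count;
- where the extension is used, the unextended BZA-raloxifene result is reported beside it;
- *very unlikely* is removed for raloxifene or replaced by the observed count.

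Analyses in population (a) stay unchanged. It would also help to say whether the 8.1.4 subgroup is the same as population (b).

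The cost is SAP wording and slightly more reporting. The unextended BZA-raloxifene estimate will be imprecise if new raloxifene users are few.
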